## Safety Reporting

## 6.1 Adverse Events (AEs)/ Serious Adverse Events (SAEs)

All AEs/SAEs occurring during the study observed by the investigator or reported by the participant, attributed to the study, will be recorded on the CRF. The relationship of AEs/SAEs to the study will be assessed by a medically qualified investigator.

AEs will be recorded on the AE Record Sheet and periodically discussed by the study steering group committee as required. Any safety concerns arising from the team will be reported to the Sponsor as soon as possible.

All SAE information must be recorded on an SAE form and sent to the Sponsor using the appropriate reporting form and the contact details on there within 24 hours of the study team being made aware of the SAE.

Any adverse event/serious adverse event occurring whilst a participant is continuing in the study, whether or not attributed to the study, will be documented in the study publication.

v 1.0

Date:

20/03/2019

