### 1.2.3 Study treatment interventions

This will be a randomised control trial with an intervention group and a control group.

1) Intervention group: Participants randomised to the intervention group will receive the standard information leaflet and will be invited to attend two group-based structured education sessions. These education sessions will be delivered by trained facilitators approximately two weeks apart. The participants will receive 82 physical activity related text messages at different weekly frequencies following the second education session up until the 12 month follow-up assessment.

These structured education sessions have been developed and refined in conjunction with PPI work and through the use of existing infrastructure consisting of Diabetes. Education and Self-Management in on-going and Newly Diagnosed (DESMOND) groups and a network of trained facilitators.

2) Control group: Participants randomised to control group will not receive the intervention. Participants will be provided with general health advice in the form of a standard information leaflet and will continue with their 'usual' GP care.

Date:

20/03/2019

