### Clinical Trials Unit

#### 1.2.4 Inclusion Criteria

- Aged 18 years or older
- 12-36 months post confirmed diagnosis of a cardiac event (myocardial infarction, angina or acute coronary syndrome)
- Able to speak and read English to participate effectively in a group education programme
- Willing and able to attend the education sessions and clinic visits
- Willing and able to give informed consent.
- Access to a mobile phone in order to receive text messages
- Willingness to allow GP notification of their participation in study and access to patient records for purpose of study
- Able to take part in moderate physical activity as assessed using Incremental Shuttle Walk Test (ISWT) (Level three or above)

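### SAP section 6.1 restricts CRF recording to adverse events attributed to the study but promises to publish all events, and does not name the source of the published data

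*SAP*

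**What the plan says.** All the safety text is in SAP section 6.1, which makes five relevant statements.

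- **CRF recording.** Events seen by the investigator or "reported by the participant, attributed to the study, will be recorded on the CRF".
- **Causality.** "The relationship of AEs/SAEs to the study will be assessed by a medically qualified investigator".
- **AE route.** "AEs will be recorded on the AE Record Sheet and periodically discussed by the study steering group committee as required".
- **SAE route.** "All SAE information must be recorded on an SAE form and sent to the Sponsor", within 24 hours of the study team becoming aware of it.
- **Publication.** Any AE or SAE arising while the participant continues in the study, "whether or not attributed to the study, will be documented in the study publication".

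The section specifies no safety table and no comparison of events between arms.

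**The concern.** The first and last statements set different scopes. Under the first, an event enters the CRF only if it is attributed to the study. Under the last, attribution makes no difference to whether the event is published. Both are current text, so at least one of them has to change.

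What is at stake is the completeness of the safety data. Participants are 12 to 36 months past a cardiac event, and the primary objective in section 1.1.1 is to raise physical activity in order to reduce later cardiovascular events. A cardiac event that nobody attributes to the study is therefore still of direct interest, and it is the kind of event that the CRF rule leaves out. If attribution governs what is recorded, the recorded events also depend on a judgement that may be made differently in the two arms of an intervention participants can see they are receiving.

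**Working it through.** No arithmetic applies: the SAP gives no adverse event rates and the point does not depend on sample size or power. The check is a reading of the section 6.1 statements against each other.

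| Statement in section 6.1 | Events covered | Attribution filter stated? | Named as source for publication? |
|---|---|---|---|
| CRF recording | AEs and SAEs | Yes, attributed only | No |
| AE Record Sheet | AEs | No | No |
| SAE form | SAEs | No | No |
| Publication | AEs and SAEs | No, all events | Not applicable |

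1. **CRF against publication.** Attributed events are a subset of all events. A report built from the CRF as described would omit every unattributed event, so it could not meet the publication commitment.

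2. **SAEs.** All SAE information goes on an SAE form to the Sponsor, with no condition on attribution. Unattributed SAEs therefore have a stated recording route in both arms.

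3. **Non-serious AEs.** The AE Record Sheet has no stated filter, but the SAP does not say whether the sheet is part of the CRF. If it is, the filter in the opening sentence applies to it and unattributed non-serious AEs have no recording route. If it is separate, they do have one.

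4. **Source of the published data.** The uses given for the two forms are discussion by the steering group and notification of the Sponsor. Neither form is linked to the publication.

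5. **Order of steps.** Read literally, an event must be attributed before it reaches the CRF, while attribution is what the medical assessment decides. The SAP does not say who would apply the first judgement. The causality sentence covers AEs and SAEs without qualification, which suggests that unrelated events were also meant to be seen.

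6. **Arms.** Section 1.2.3 gives the intervention arm two group sessions and 82 text messages, whereas "Participants randomised to control group will not receive the intervention". Fewer study activities in controls means fewer occasions on which an event could be attributed to the study, so a filter would probably remove a larger share of control events. The share is not zero retained: the rule refers to the study, not the intervention, and controls also perform the Incremental Shuttle Walk Test (ISWT), an entry requirement in section 1.2.4 and an outcome at baseline and 12 months in section 2.2.

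**The case against.** The strongest reply is that this is loose drafting. Section 6.1 provides two recording routes without a filter, the causality assessment makes sense only if unrelated events are captured, and the publication commitment already covers everything. Event capture is also commonly left to the protocol, to which section 1 refers the reader for operational detail.

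Much of this stands, and it rules out three stronger readings that a reader might infer.

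- *That the promised report cannot be produced at all.* This does not follow, because the SAE form and AE Record Sheet may hold the unattributed events. In particular, the text does not support a conclusion that unattributed SAEs would disappear.
- *That control events would be close to zero by construction.* Controls undergo study procedures, including the ISWT, and can have events attributed to the study.
- *That a planned comparison of arms is biased.* The SAP plans no such comparison. Published events in a two-arm trial will nevertheless be read by arm, so unequal ascertainment remains a reasonable concern.

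The reply does not remove the contradiction. Whatever the protocol says, the two sentences in the SAP disagree, and an unfiltered reading of the forms puts the opening sentence at odds with the middle paragraphs as well.

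**Conclusion.** The point holds as an internal contradiction with a gap beside it: the recording rule for the CRF is narrower than the publication rule, and the SAP names no other source for the published safety data. The consequence is conditional. If the filter is applied, and if the AE Record Sheet falls under it, unattributed non-serious AEs would be lost, probably in greater proportion among controls. If both forms sit outside the filter and capture everything, the problem reduces to wording and to naming the source.

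No number can be attached to the loss without event rates and attribution rates, and the SAP gives neither. The greater loss in controls is an inference from the difference in study contact between the arms. The protocol was not available for this point and may define the recording scope. The primary analysis is unaffected.

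**What to change.** Reconcile the two sentences in section 6.1 as follows.

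1. Delete the attribution condition from the CRF recording rule, so that all AEs and SAEs observed or reported during the study are recorded in both arms. Keep the section's own period, the study, and do not start the window at randomisation. The ISWT is an entry requirement, so an event at the baseline test could otherwise be missed.
2. Make relatedness a data field completed at the medical assessment, not a condition for entry.
3. Name the form or forms from which the published safety data will be drawn, and say whether the AE Record Sheet is part of the CRF.
4. Report all-cause and related events by arm. This adds to the plan and is not the correction of an error, but it makes the publication commitment usable.

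The cost is a few sentences in the SAP, a small amount of extra data entry, and a check that the protocol and CRF carry the same rule. Section 1 says the SAP will be finalised before database lock. The check on what the forms capture should come as early as possible, because events left unrecorded during follow-up may be hard to recover.
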